5.3.3.2 Immune-related Hepatitis

Monitor subjects for abnormal liver tests prior to and periodically during treatment. For Grade 1 elevations of AST, ALT, and/or total bilirubin, monitor laboratory values 1 to 2 times per week. For Grade 2 elevations of AST, ALT, and/or total bilirubin, hold study treatment, recheck laboratory values and increase frequency of monitoring to every 3 days; administer corticosteroid 0.5 to 1 mg/kg per day (prednisone or equivalent) if the abnormal elevation persists with significant clinical symptoms in 3 to 5 days. Study treatment may be resumed only when symptoms improve to \leq Grade 1 and corticosteroid dose is \leq 10 mg per day. Taper over at least 1 month. Subjects should be advised to stop unnecessary medications and any known hepatotoxic drugs. For Grade 3 hepatitis, immediately start corticosteroid 1 to 2 mg/kg per day methylprednisolone or equivalent. Increase frequency of monitoring to every 1 to 2 days. If corticosteroid refractory or no improvement after 3 days, consider mycophenolate mofetil or azathioprine (if using azathioprine, test for thiopurine methyltransferase deficiency). Measure laboratory parameters at least daily or every other day; consider inpatient monitoring for subjects with AST/ALT $>8 \times$ ULN and/or elevated total bilirubin $3 \times$ ULN. Corticosteroid taper can be attempted around 4 to 6 weeks; re-escalate if needed; optimal duration unclear. For Grade 4 hepatitis, administer 2 mg/kg per day methylprednisolone equivalents and follow guidance for Grade 3.

Permanently discontinue for Grade 3 or Grade 4 immune-related hepatitis.

Infliximab might not be the most appropriate treatment option in the situation of immune-related hepatitis given the potential risk of idiosyncratic liver failure.

5.3.3.3 Immune-related Pneumonitis

Monitor subjects for signs and symptoms of pneumonitis. Subjects with Grade 1 pneumonitis should be monitored weekly and treatment should be held if there is radiographic evidence of pneumonitis progression. Treatment may be resumed with radiographic evidence of improvement or resolution. If no improvement, should treat as Grade 2. Subjects should be monitored weekly. For Grade 2 pneumonitis, recommend treatment with corticosteroids at a dose of 1 to 2 mg/kg per day prednisone equivalents, followed by a corticosteroid taper by 5 to 10 mg per week over 4 to 6 weeks. Consider bronchoscopy with bronchoalveolar lavage and empirical antibiotics. Monitor every 3 days. If no improvement after 48 to 72 hours of prednisone, treat as Grade 3. For Grade 3 pneumonitis, empirical antibiotics and corticosteroids (prednisolone IV 1 to 2 mg/kg per day) should be administered. If no improvement after 48 hours, may add 5 mg/kg infliximab or mycophenolate mofetil IV 1 g twice a day or IV immunoglobulin for 5 days or cyclophosphamide; taper corticosteroids over 4 to 6 weeks. Pulmonary and infectious disease consults should be sought if necessary. Subjects should be hospitalized for further management.

Withhold study treatment for Grade 2 immune-related pneumonitis and permanently discontinue treatment for Grade 3 or 4 or recurrent pneumonitis upon restarting study treatment.

5.3.3.4 Immune-related Hypothyroidism and Hyperthyroidism

Monitor thyroid function prior to and periodically (test for thyroid-stimulating hormone [TSH] and free thyroxine (FT4) every 4 to 6 weeks and as clinically indicated) during treatment.

For Grade 1 hypothyroidism, treatment may be continued with close follow-up and monitoring of TSH and FT4. For Grade 2 hypothyroidism, treatment should be withheld, thyroid hormone supplementation prescribed for symptomatic subjects with any degree of TSH elevation or in asymptomatic subjects with TSH levels that persist >10 mIU/L (measured 4 weeks apart). Endocrinology consult should be considered. For Grade 3 hypothyroidism, treatment should be held, supplementation prescribed, and endocrinology consult obtained. For Grade 4 hypothyroidism, treatment should be permanently discontinued, supplementation prescribed, and endocrinology consult obtained. May admit for IV therapy if signs of myxedema (bradycardia, hypothermia).

For Grade 1 hyperthyroidism, may continue treatment with close follow-up and monitoring of TSH and FT4 every 2 to 3 weeks until it is clear whether there will be persistent hyperthyroidism. For Grade 2 hyperthyroidism, study treatment should be held, medical management initiated, and endocrinology consultation considered. For persistent hyperthyroidism (>6 weeks) or clinical suspicion, a workup for Graves' Disease should be initiated. For Grade 3 hyperthyroidism, treatment should be held, medical management initiated, and endocrinology consulted. For Grade 4 hyperthyroidism, treatment should be permanently discontinued, supplementation prescribed, and endocrinology consult obtained. For severe

symptoms or concern for thyroid storm, should hospitalize subject and initiate prednisone 1 to 2 mg/kg per day or equivalent tapered over 1 to 2 weeks. May also use saturated solution of potassium iodide or thionamide (methimazole or propylthiouracil).

Consider that thyroiditis is transient and within weeks resolves to primary hypothyroidism or normal. Graves' Disease is generally persistent and due to increased thyroid hormone production that can be treated with antithyroid medical therapy.

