5.3.1 Dose Modification for Adverse Events

The following guidance is for dose modification of CX-072 and/or ipilimumab (ie, study treatment). Delays or permanent discontinuation of study treatment may be required as outlined in [Table 5](#) and [Section 5.3.2](#). Dose reduction of any study treatment is not permitted. Guidance is adapted from American Society of Clinical Oncology Clinical Practice Guidelines ([Brahmer 2018](#)), which should be referenced for additional detail and information when assessing and managing AEs that are considered to be potentially immune related.

Additional recommendations for interventions of irAEs depending on severity of the event are provided in [Section 5.3.3](#).

Table 5 Dose Modifications for Select Adverse Events

Adverse Event	Grade 1	Grade 2	Grade 3	Grade 4
Skin toxicities including dermatitis, Stevens-Johnson syndrome, or toxic epidermal necrolysis See also Section 5.3.3.11	No action; G1 does not apply to severe cutaneous toxicities (eg, Stevens-Johnson syndrome, toxic epidermal necrolysis).	Hold until recovery to \leq G1 or baseline.	Hold until recovery to \leq G1 or baseline. Consult with a dermatologist.	Permanently discontinue study treatment.
Colitis ^a See also Section 5.3.3.1	No action; may consider holding study treatment and resuming if toxicity does not exceed G1	Hold until recovery to \leq G1. Consider permanent discontinuation of ipilimumab. ^b	Hold until recovery to \leq G1. Consider permanent discontinuation of ipilimumab. ^b	Permanently discontinue study treatment.
Increased serum transaminases (AST/ALT) or total bilirubin See also Section 5.3.3.2	No action; monitor laboratory values 1 to 2 times per week.	Hold until recovery to \leq G1 or baseline on prednisone \leq 10 mg per day.	Permanently discontinue study treatment.	Permanently discontinue study treatment.
Pneumonitis See also Section 5.3.3.3	No action	Hold until recovery to \leq G1.	Permanently discontinue study treatment	Permanently discontinue study treatment.
Hypothyroidism or hyperthyroidism See also Section 5.3.3.4	No action	Hold until recovery to \leq G1 or baseline.	Hold until recovery to \leq G1 or baseline (with hormone replacement for hypothyroidism).	Permanently discontinue study treatment.

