5.3.3.1 Immune-related Colitis

Counsel subject to inform the Investigator of any abdominal pain, nausea, cramping, blood or mucus in stool or changes in bowel habits, fever, abdominal distention, obstipation, or constipation.

For Grade 1 events, consider temporary withholding of treatment to confirm toxicity does not exceed Grade 1. Withhold study treatment for Grade 2 or 3 immune-related colitis. For moderate

(Grade 2) colitis administer corticosteroids, unless diarrhea is transient, starting with initial dose of 1 mg/kg per day prednisone or equivalent. Gastroenterology should be consulted and should consider permanent discontinuation of ipilimumab. For severe (Grade 3) or life-threatening (Grade 4) colitis, administer corticosteroids at a dose of 1 to 2 mg/kg per day prednisone equivalents (for Grade 3) or 1.0 to 2 mg/kg per day methylprednisolone equivalents (for Grade 4) followed by corticosteroid taper. If Grade 3 symptoms persist for ≥ 3 to 5 days or recur after improvement, consider administering IV corticosteroid or noncorticosteroid (eg, infliximab). Consider colonoscopy/GI endoscopy in cases where subjects have been on immunosuppression and may be at risk for opportunistic infections as an independent cause for diarrhea (ie, CMV colitis) and for those who are anti-TNF or corticosteroid refractory. When symptoms improve to \leq Grade 1, taper corticosteroids over at least 4 to 6 weeks before resuming treatment, although resuming treatment while on low-dose corticosteroid may also be an option after an evaluation of the risks and benefits. Permanently discontinue treatment for Grade 4 or recurrent colitis upon restarting study treatment.

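### Section 5.3.3.4 orders supplementation for Grade 4 hyperthyroidism, and 4 of the 10 permanent stops in Section 5.3.3 are missing from Table 5, most directly recurrent colitis and recurrent pneumonitis.

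*Combined protocol and SAP*

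**What the plan says.** **Thyroid.** For the most severe grade of thyroid overactivity, Section 5.3.3.4 states: "For Grade 4 hyperthyroidism, treatment should be permanently discontinued, supplementation prescribed, and endocrinology consult obtained". One grade lower, the same section states: "For Grade 3 hyperthyroidism, treatment should be held, medical management initiated, and endocrinology consulted". Grade 2 hyperthyroidism is also assigned medical management. In Table 5 (Section 5.3.1), the thyroid row covers both conditions, and its Grade 3 cell qualifies recovery as "with hormone replacement for hypothyroidism".

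**Colitis.** Section 5.3.3.1 states: "Permanently discontinue treatment for Grade 4 or recurrent colitis upon restarting study treatment". For Grades 2 and 3, Table 5 says to hold until recovery to Grade 1 or less and adds: "Consider permanent discontinuation of ipilimumab". It has no rule for recurrence.

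**Pneumonitis.** Section 5.3.3.3 tells sites to "permanently discontinue treatment for Grade 3 or 4 or recurrent pneumonitis upon restarting study treatment". Table 5 gives no action at Grade 1, a hold at Grade 2 and a permanent stop at Grades 3 and 4, again with no rule for recurrence.

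**Myocarditis and encephalitis.** Section 5.3.3.5 requires a permanent stop for myocarditis above Grade 2. Section 5.3.3.10 requires one once autoimmune encephalopathy is confirmed. The Table 5 rows ask the site to hold treatment and discuss discontinuation with the Sponsor Medical Monitor.

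**How the rules are linked.** Section 5.3.1 sends the reader to Table 5 and Section 5.3.2 for delays and permanent stops, and describes Section 5.3.3 as additional recommendations. Section 5.3.2 refers back to Table 5. The sentence on resuming treatment, below Table 5, leaves restart after recovery to the investigator, with exceptions only for what Table 5 and Section 5.3.3.12 state.

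**The concern.** These are instructions that a site acts on for an individual patient, so the wording has to be right and has to agree wherever it appears.

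The hyperthyroidism sentence repeats the Grade 4 hypothyroidism action. In this section supplementation means thyroid hormone, so a literal reading adds hormone in a life-threatening state of hormone excess.

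The second problem is that a site working from Table 5 and the resumption sentence can reach a different decision from a site working from Section 5.3.3. After a second episode of Grade 2 or 3 colitis, or of Grade 2 pneumonitis, one site would hold and consider restarting while the other would stop for good, and each could cite the protocol. The trial combines two checkpoint inhibitors in up to 162 subjects at about 40 sites, so differing readings are plausible.

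**Working it through.** No sample size, power or error rate is involved. The check is a comparison of texts and a count.

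**Step 1: what supplementation means in Section 5.3.3.4.** The Grade 2 hypothyroidism sentence names thyroid hormone, given for raised TSH. The Grade 3 and Grade 4 hypothyroidism sentences repeat the requirement in short form. Hyperthyroidism at Grades 2 and 3 gets medical management instead. The text after the Grade 4 hyperthyroidism sentence gives prednisone, potassium iodide or a thionamide for severe symptoms or thyroid storm. Only the Grade 4 hyperthyroidism sentence departs from this pattern, and its action is word for word that of Grade 4 hypothyroidism. The likeliest explanation is a carry-over. The permanent stop in that sentence agrees with Table 5; only the supplementation clause is wrong.

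**Step 2: the permanent stops in Section 5.3.3.** Counting rule: one per condition and trigger, grades joined in one phrase count once, and wording that only asks to consider or discuss stopping is left out.

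| # | Mandatory stop | Section | Also mandatory in Table 5? |
|---|---|---|---|
| 1 | Colitis, Grade 4 | 5.3.3.1 | Yes |
| 2 | Colitis, recurrent after restart | 5.3.3.1 | No |
| 3 | Hepatitis, Grade 3 or 4 | 5.3.3.2 | Yes |
| 4 | Pneumonitis, Grade 3 or 4 | 5.3.3.3 | Yes |
| 5 | Pneumonitis, recurrent after restart | 5.3.3.3 | No |
| 6 | Hypothyroidism, Grade 4 | 5.3.3.4 | Yes |
| 7 | Hyperthyroidism, Grade 4 | 5.3.3.4 | Yes |
| 8 | Myocarditis above Grade 2 | 5.3.3.5 | No (hold and discuss) |
| 9 | Uveitis or episcleritis, Grade 3 or 4 | 5.3.3.9 | Yes |
| 10 | Autoimmune encephalopathy, confirmed | 5.3.3.10 | No (hold and discuss) |

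Sections 5.3.3.6, 5.3.3.7, 5.3.3.8, 5.3.3.11 and 5.3.3.12 state no permanent stop. The total is 6 + 4 = 10, so 4 of 10 are absent from Table 5.

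**Step 3: sensitivity to the counting unit.** Splitting each Grade 3 or 4 pair (hepatitis, pneumonitis, ocular, and myocarditis above Grade 2) adds 4 entries, giving 10 + 4 = 14. One of the added entries is myocarditis, so the missing count is 4 + 1 = 5, or 5 of 14. The four missing triggers are the same.

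**Step 4: whether another rule fills the gap.**
- Section 5.3.3.12, the only subsection excepted by the resumption sentence, contains 0 of the 4.
- The catch-all Grade 4 row of Table 5 excludes reactions already listed in the table.
- Table 5 does state comparable stops in other rows: confirmed Guillain-Barré syndrome or myasthenia gravis at any grade, and Grade 3 nephritis. A reader could therefore take its silence on the 4 as intended.

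**Step 5: where the two texts lead to different actions.** The Table 5 cells that say to hold until recovery, where Section 5.3.3 requires a stop on recurrence, are colitis Grade 2, colitis Grade 3 and pneumonitis Grade 2: 3 cells. The recurrence rules carry no grade limit, so the Grade 1 cells for colitis and pneumonitis are also silent, giving 3 + 2 = 5 cells on the widest reading.

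**Step 6: pointers.** All 4 affected rows cite the correct subsection, for example "Pneumonitis See also Section 5.3.3.3". Two other rows do not: creatinine cites Section 5.3.3.5 (myocarditis) and pancreatitis cites Section 5.3.3.10 (encephalitis).

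**The case against.** The strongest reply is that nothing here would mislead a competent site. Section 5.3.3 opens by requiring standard-of-care management and citing a published guideline for immune-related events. The faulty thyroid sentence itself requires an endocrinology consult, and antithyroid treatment follows within the same paragraph. It says supplementation without naming thyroid hormone.

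On the stops, Table 5 is a summary whose rows point to the right subsections, and those pointers can be read as part of what the table states. The resumption sentence is permissive while the Section 5.3.3 stops are mandatory, so a site can obey both by stopping. Section 5.3.2 does not claim that Table 5 is the only source: Sections 4.11, 5.3.2 and 5.3.4.2 add stops of their own, and Section 4.11 requires stopping for any adverse event that makes further dosing unsafe. For myocarditis and encephalitis, hold-and-discuss can be read as the step before the stop, which would leave 2 of 10 as the real gap.

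Much of this stands as mitigation. The pointers are correct, the myocarditis and encephalitis gaps are weaker, and a careful site will find the stops. It does not remove the defect. The surrounding text softens the supplementation instruction without withdrawing it, and the section gives that word no other meaning. The links between sections bypass Section 5.3.3 when they say where stops are found and when they list exceptions to restart, and Section 5.3.1 presents it as recommendations. That both texts can be obeyed by stopping does not help a patient whose site relies on the permission to restart.

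**Conclusion.** The concern holds. The Grade 4 hyperthyroidism instruction is wrong as written. Four of the 10 permanent stops in Section 5.3.3 (5 of 14 if grade pairs are split) are absent from Table 5 and from the exceptions to the resumption rule. The direct conflict is narrower: recurrent colitis and recurrent pneumonitis, in 3 cells that say hold until recovery. Myocarditis and encephalitis lack a mandatory stop in the table, but the required discussion with the Medical Monitor limits restart.

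The documents give no rates for these recurrences or for Grade 4 hyperthyroidism, so the number of patients affected cannot be estimated; it is probably small. The consequence is for individual patient safety. Sample size and the primary analyses are unaffected. The conclusion rests on reading supplementation as thyroid hormone, as the section uses it, and on reading the resumption sentence literally. The change should be made, because the risk falls on patients and the correction is only wording.

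**What to change.** 1. Section 5.3.3.4: for Grade 4 hyperthyroidism, keep the permanent stop and the endocrinology consult, and replace the supplementation clause with initiation of medical management, matching Grades 2 and 3.
2. Table 5: add a permanent stop on recurrence after restart to the colitis and pneumonitis rows, a permanent stop above Grade 2 to the myocarditis row, and a permanent stop on confirmed autoimmune encephalopathy to the encephalitis row.
3. Resumption sentence below Table 5: widen the exception from Section 5.3.3.12 to the whole of Section 5.3.3.
4. Section 5.3.2: name Section 5.3.3 beside Table 5 as a source of permanent stops.
5. Clerical: correct the cross-references in the creatinine and pancreatitis rows.

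Items 2 to 4 carry the protocol's own Section 5.3.3 rules into the places where sites will look and create no new stop. The cost is wording in one protocol amendment, with no change to sample size, visits or analyses.

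### Section 5.3.3.4 gives Grade 4 hyperthyroidism the Grade 4 hypothyroidism instruction, so supplementation is directed for a state of thyroid hormone excess

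*Combined protocol and SAP*

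**What the plan says.** Table 5 in Section 5.3.1 has one row for hypothyroidism and hyperthyroidism together. At Grade 4 it requires permanent discontinuation of study treatment, and the row refers sites to Section 5.3.3.4 for management.

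Section 5.3.3.4 handles the two conditions in consecutive paragraphs. For the underactive gland at the highest grade it says: "For Grade 4 hypothyroidism, treatment should be permanently discontinued, supplementation prescribed, and endocrinology consult obtained". For the overactive gland at the same grade it says: "For Grade 4 hyperthyroidism, treatment should be permanently discontinued, supplementation prescribed, and endocrinology consult obtained".

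The section specifies the kind of supplementation once, at Grade 2 hypothyroidism: "thyroid hormone supplementation prescribed for symptomatic subjects with any degree of TSH elevation". At the lower hyperthyroidism grades the wording differs: "For Grade 2 hyperthyroidism, study treatment should be held, medical management initiated, and endocrinology consultation considered" and "For Grade 3 hyperthyroidism, treatment should be held, medical management initiated, and endocrinology consulted".

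**The concern.** Hyperthyroidism is an excess of thyroid hormone. An instruction to supplement, in a section where supplementation means thyroid hormone, points the wrong way. The sentence sits in patient-management text that Table 5 sends sites to, and it covers the most severe grade of hyperthyroidism the section addresses. Section 9.7 lists hyperthyroidism among the example immune-related events of special interest for this two-checkpoint-inhibitor regimen, so the guidance is not hypothetical. What is at stake is the correctness of a safety instruction. No estimate, test or sample size depends on it.

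**Working it through.** No figure in the plan is involved, so the check is a comparison of text.

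**Step 1: the two paragraphs of Section 5.3.3.4, grade by grade.**

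| Grade | Hypothyroidism | Hyperthyroidism |
|---|---|---|
| 1 | Continue, monitor | Continue, monitor |
| 2 | Withhold; thyroid hormone supplementation under stated TSH or symptom conditions | Hold; medical management |
| 3 | Hold; supplementation; endocrinology consult | Hold; medical management; endocrinology consult |
| 4 | Discontinue permanently; supplementation; endocrinology consult | Discontinue permanently; supplementation; endocrinology consult |

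The two columns prescribe different treatment at Grades 2 and 3 and become identical at Grade 4.

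**Step 2: what supplementation means here.** The word appears 4 times in Section 5.3.3.4: 3 for hypothyroidism (Grades 2, 3 and 4) and 1 for hyperthyroidism (Grade 4). The medical-management phrase appears 2 times, both for hyperthyroidism (Grades 2 and 3). Elsewhere in the readable text, supplementation appears 2 times in Section 4.6 (exclusion criterion 9, on hormone deficiency) and 1 time in Section 9.7 (systemic hormonal supplementation, as one way an event qualifies as immune-related). The total is 4 + 2 + 1 = 7, and every use that names a kind refers to hormones. The Section 9.7 use is a general definition whose examples include hyperthyroidism, so it supports the hormonal meaning of the word but does not show which thyroid condition is to be supplemented.

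**Step 3: the rest of the hyperthyroidism guidance.** Directly after the Grade 4 sentence, the section says that for severe "symptoms or concern for thyroid storm, should hospitalize subject and initiate prednisone 1 to 2 mg/kg per day". It then allows potassium iodide or a thionamide. It closes by attributing Graves' disease to overproduction of thyroid hormone, treatable with antithyroid drugs. None of this involves supplementation.

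**Step 4: Table 5.** The Grade 4 cell agrees with the sentence on permanent discontinuation and says nothing on supplementation, so the table does not contradict it. The Grade 3 cell mentions hormone replacement only in connection with hypothyroidism, which is indirect support.

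**Result.** Of the 3 hyperthyroidism grades with a treatment directive (2, 3 and 4), 1 carries the hypothyroidism wording.

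**The case against.** The strongest reply has four parts.

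- **Status of the text.** Section 5.3.1 introduces this material as additional recommendations, and Section 5.3.3.12 says recommended treatment will be refined as the study progresses. The study-drug action at Grade 4 comes from Table 5 and is correct. This limits the weight of the error, but a recommendation should still be right.
- **Correct treatment follows at once.** A Grade 4 case would ordinarily present with severe symptoms, and the thyroid-storm sentences would then guide care. The endocrinology consult is required in the disputed sentence itself. Sections 5.3.1 and 5.3.3 also refer sites to a published guideline, and Section 5.3.3 to standard of care. All of this stands and makes harm unlikely. It does not correct the instruction.
- **A charitable reading exists.** The sentence does not name thyroid hormone, and the section notes: "Consider that thyroiditis is transient and within weeks resolves to primary hypothyroidism or normal". Supplementation could mean replacement after that transition. But the sentence states no such condition or delay; it lists supplementation beside discontinuation and the consult as a response to Grade 4 hyperthyroidism. If some other supplement were meant, a site could not tell which, and the sentence would still need correcting.
- **The proposed wording is general.** Medical management is less specific than the thyroid-storm text. That is a fair drafting point for the sponsor's medical team.

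**Conclusion.** The point holds. The Grade 4 hyperthyroidism sentence is wrong as written and conflicts with the section's own treatment of hyperthyroidism. The expected impact is low: one phrase, at one of three grades, with safeguards beside it. The documents give no rate for Grade 4 hyperthyroidism, so none is assumed; that few if any of the up to 162 subjects (Section 3.2) would be affected is a judgement, not a calculation.

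The conclusion rests on reading supplementation in its only sense described in the section, thyroid hormone. That the phrase was copied from the hypothyroidism paragraph is an inference, and the conclusion does not depend on it. It should be fixed because it is a safety instruction, but it is not a reason to pause the study.

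**What to change.** In the Grade 4 hyperthyroidism sentence of Section 5.3.3.4, replace the supplementation phrase with the medical-management phrase used at Grades 2 and 3. Keep permanent discontinuation and the endocrinology consult. The sponsor's medical team should confirm the wording and may prefer to link Grade 4 explicitly to the thyroid-storm guidance that follows. If later hormone replacement after thyroiditis is intended, state it as a separate, conditional sentence.

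The cost is one phrase in the next amendment. Visits, design, sample size, endpoints and analyses are unaffected.
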